5.4.4.4.6. MACE

Based on the PAS, treatment emergent MACEs are summarized by presenting, per treatment group, the number and percentage of subjects having any MACE, and having an event of the MACE subcategories (cardiovascular death, non-fatal myocardial infarction, non-fatal stroke. A listing of all events referred to the MACE adjudication committee (whether adjudicated to be MACE or not) is prepared for AP3 on the PAS.

5.4.5. Additional Safety Assessments

5.4.5.1. Clinical Laboratory Tests

Safety laboratory samples for hematology, blood chemistry, and urinalysis are taken at all scheduled visits. The samples are centrally analyzed by ACM or by local laboratories when necessary, and the results are electronically transferred to Actelion. The following parameters are planned to be collected as per protocol:

- **Hematology**: red blood cell count, total and differential white blood cell counts (basophils, eosinophils, lymphocytes, monocytes, neutrophils, band forms), platelet count, hemoglobin, hematocrit, mean corpuscular hemoglobin, mean corpuscular volume.
- **Blood chemistry**: Glucose (preferably under fasting conditions), alanine and aspartate aminotransferase (ALT, AST), alkaline phosphatase, total bilirubin, lactate dehydrogenase, creatinine, urea, cholesterol, triglycerides, sodium, potassium, chloride, calcium, total protein, albumin, C-reactive protein.
- Urine/serum pregnancy test (from visits E4 to EOT2 or EOT3 and at Follow-up visit E2 or Follow-up visit 2 [FU2], as applicable).

All laboratory results are stored in SDTM201.LB/SDTM202.LB together with nominal visit and timepoint information. The two LB datasets are concatenated for the purposes of derivations and analysis.

As per study protocol, urinalysis results were to be collected and recorded only if an abnormality/ finding would constitute an (S)AE. The limited number of available data does not allow for performing the planned analyses (i.e., change in urinalysis parameters) as described in Section 3.10.2 of the protocol, and therefore will not be presented in the final CSR.

This approach would also apply to pregnancy test results not collected in CRF.

Numerical results are converted into both conventional and SI units as per Quality system document OTH-000005 (Definition of Marked Abnormalities in Laboratory Data). Results reported as below the lower limit of quantification (LLOQ) are set to the LLOQ value. Results reported as > XX are set to XX for calculation of summary statistics.

All analyses are based on the standardized SI values.

The ponesimod baseline value (as described in Section 5.1.2) is flagged in the AdaM dataset.

Absolute and percentage change from ponesimod baseline are derived for all post-baseline assessments.

All nominal visits are re-windowed based on the visit schedule in Section 5.1.7.

Flags are derived according to project specific ranges for marked laboratory abnormalities as described in Section 6.7 (Appendix 8). Marked laboratory abnormalities are flagged to indicate the increasing severity of abnormally low ("LL", "LLL"), or high values ("HH", and "HHH") for each of the laboratory parameters listed.

In addition, the following abnormality flags are derived for ALT, AST, total bilirubin (TBIL), and alkaline phosphatase (ALP):

- ALT: ≥ 1 × upper limit of normal range (ULN), ≥ 3 × ULN, ≥ 5 × ULN, ≥ 8 × ULN, ≥ 10*ULN, ≥ 20*ULN;
- AST: $\geq 1 \times ULN$, $\geq 3 \times ULN$, $\geq 5 \times ULN$, $\geq 8 \times ULN$, $\geq 10 \times ULN$, $\geq 20 \times ULN$;
- ALT or AST: $\geq 3 \times ULN$, $\geq 5 \times ULN$, $\geq 8 \times ULN$, $\geq 10 \times ULN$, $\geq 20 \times ULN$;
- TBIL $\geq 2 \times ULN;$
- ALT or AST \ge 3 × ULN and TBIL \ge 2 × ULN (at the same sample date);
- ALT or AST \ge 3 × ULN and TBIL \ge 2 × ULN + AP < 2 × ULN (at the same sample date).

The following summaries will be produced for quantitative laboratory results by treatment group:

- Summary of absolute values for laboratory parameters: descriptive statistics by analysis visit (AP3 on the PAS);
- Summary of absolute values and absolute change from ponesimod baseline values for laboratory parameters: descriptive statistics by analysis visit (AP3 on the PAS);
- Summary of absolute values for ALT, AST, bilirubin and ALP: descriptive statistics by analysis visit (AP3on the PAS);
- Summary of absolute values for lymphocytes: descriptive statistics by analysis visit (AP3 on the PAS);
- Summary of absolute values and absolute change from ponesimod baseline values for ALT, AST, bilirubin and ALP: descriptive statistics by analysis visit (AP3 on the PAS);
- Summary of absolute values and absolute change from ponesimod baseline values for lymphocytes: descriptive statistics by analysis visit (AP3 on the PAS);
- Summary of percent change from ponesimod baseline values for lymphocytes: descriptive statistics by analysis visit (AP3 on the PAS);
- Summary of absolute values at ponesimod baseline, at last on-treatment and at each followup visit (FU7, FU30, FU90 and Last FU) for lymphocytes (completed/discontinued subjects with at least one follow-up value only): descriptive statistics (AP3 on the PAS); by Post-Treatment DMT subgroup ((Any DMT, including ponesimod), No DMT).
- Summary of percent change from ponesimod baseline to last on-treatment and to each follow-up visit (FU7, FU30, FU90 and Last FU) for lymphocytes (completed/discontinued subjects with at least one follow-up value only): descriptive statistics (AP3 on the PAS); by Post-Treatment DMT subgroup ((Any DMT, including ponesimod), No DMT).
- Incidence of treatment-emergent marked laboratory abnormalities (LL, LLL, HH, HHH) as defined in Section 6.8 (Appendix 8): frequency counts and percentages, where percentages are based on the number of subjects with at least one treatment-emergent post-baseline value for the specific parameter during the analysis period (i.e., number of subjects at risk; AP3 on the PAS);
- Incidence of treatment-emergent special laboratory abnormalities for ALT, AST, Bilirubin and ALP: frequency counts and percentages, where percentages are based on the number of subjects with at least one treatment-emergent post-baseline value during the analysis period (i.e., number of subjects at risk; AP3 on the PAS).

The following plots are produced for quantitative laboratory results by treatment group:

- Plot of percent change from ponesimod baseline values for lymphocytes: mean ± SE by analysis visit (AP3 on the PAS).
- Plot of absolute values at ponesimod baseline, at last on-treatment and at each follow-up visits (FU7, FU30, FU90 and Last FU) for lymphocytes (completed/discontinued subjects with at least one follow-up value only): mean ± SE (AP3 on the PAS by Post-Treatment DMT subgroup ((Any DMT, including ponesimod), No DMT).
- Plot of percent change from ponesimod baseline to last on-treatment and follow-up visits (FU7, FU30, FU90 and Last FU) for lymphocytes (completed/discontinued subjects with at least one follow-up value only): mean ± SE (AP3 on the PAS), by Post-Treatment DMT subgroup ((Any DMT, including ponesimod), No DMT).
- A plot to evaluate Drug-Induced Serious Hepatotoxicity (eDISH plot) based on the highest observed treatment-emergent ALT and total bilirubin values. Individual subject's values expressed as × ULN are plotted on a log-log scatter plot (ALT on the horizontal axis, total bilirubin on the vertical axis); reference lines are drawn at Hy's law thresholds, i.e., at 3 × ULN for ALT and at 2 × ULN for total bilirubin. Footnote presented which provides, for each treatment group, the number and percentage of subjects falling in each of the 4 quadrants defined by these reference lines (AP3 on the PAS).
- The following listings are produced for laboratory results by treatment group and visit for AP3 on the PAS: Listings will only be produced for abnormal values for a patient for a given parameter.
 - Listing of specified abnormalities for ECG and Blood Pressure.
 - Listing of specified liver function test abnormalities;
 - Listing of marked laboratory abnormalities as specified in Appendix 8.

In addition, a listing of all lymphocyte values will also be provided.

5.4.5.2. Vital Signs and Physical Examination Findings

All vital signs results are stored in SDTM201.VS/SDTM202.VS together with nominal visit and timepoint information. The two VS datasets are concatenated for the purposes of derivations and analysis.

5.4.5.2.1. Blood pressure

Measurements of systolic (SBP) and diastolic (DBP) blood pressure (mmHg) are collected predose at all scheduled study visits. In addition, pre-dose and post-dose (1h, 2h, 3h, 4h, 5h, 6h) measurements are collected on Day 1, Day 8 and Day 15 of ponesimod administration, at reinitiation visits, and at the visit for the transition from TP2 to TP3.

The ponesimod baseline value (as described in Section 5.1.2) is flagged in the AdaM dataset.

Absolute change from ponesimod baseline are derived for all post-baseline assessments. All nominal visits (excluding **post-dose** assessments collected on Day 1, Day 8 and Day 15 of ponesimod administration and at re-initiation visits) are re-windowed based on the visit schedule in Section 5.1.7. All assessments, including post-dose assessments, are used for the derivation of "Last on treatment" and "Last follow-up" values.

For by-visit and by-hour tables presenting summary statistics of SBP and DBP results, the latest (by datetime) transmitted measurement per nominal subject-visit/timepoint is used in case of multiple data available at that visit or visit/timepoint.

Assessments meeting the following conditions are flagged in the AdaM dataset for all assessments (whether scheduled or unscheduled, and whether windowed or not):

Low blood pressure

- SBP \leq 90 mmHg or \geq 20 mmHg decrease from ponesimod baseline;
- SBP \leq 90 mmHg;
- \geq 20 mmHg decrease in SBP from ponesimod baseline;
- DBP \leq 50 mmHg or \geq 15 mmHg decrease from ponesimod baseline;
- DBP \leq 50 mmHg;
- ≥ 15 mmHg decrease in DBP from ponesimod baseline.

High blood pressure

- SBP \geq 160 mmHg or \geq 20 mmHg increase from ponesimod baseline;
- SBP \geq 160 mmHg;
- SBP \geq 140 mmHg;
- ≥ 20 mmHg increase in SBP from ponesimod baseline;
- DBP \geq 100 mmHg or \geq 15 mmHg increase from ponesimod baseline;
- DBP \geq 100 mmHg;
- DBP \geq 90 mmHg;
- ≥ 15 mmHg increase in DBP from ponesimod baseline.

Each condition listed above is flagged separately.

Pre-dose values on Day 1, Day 8 and Day 15 following first ponesimod administration and on Day 1 of a re-initiation are flagged, and absolute and percent change from pre-dose on each day are calculated for the hourly post-dose assessments.

For all hourly post-dose assessments on Day 1, 8 and 15 following first ponesimod administration and on Day 1 of a re-initiation, flags are set for the following conditions:

- SBP \leq 90 mmHg or \geq 20 mmHg decrease from pre-dose;
- ≥ 20 mmHg decrease from pre-dose in SBP;
- DBP \leq 50 mmHg or \geq 15 mmHg decrease from pre-dose;
- \geq 15 mmHg decrease from pre-dose in DBP.

Pre-dose values on Day 1, Day 8 and Day 15 following first ponesimod administration and on Day 1 of re-initiation were presented in the Interim Analysis CSR. It was determined that this was no longer required and istherefore not planned to be presented in the Final CSR.

The following summary will be produced for blood pressure abnormalities, as defined above, by treatment group:

• Incidence of treatment-emergent blood pressure abnormalities for SBP and DBP: frequency counts and percentages, where percentages are based on the number of subjects with at least one treatment-emergent post-baseline value during the analysis period (i.e., number of subjects at risk; AP3 on the PAS).

All abnormal blood pressure results are listed by treatment group and visit for AP3 on the PAS.

5.4.5.2.2. Body weight

Body weight (kg) is collected at selected scheduled visits.

The ponesimod baseline value (as described in Section 5.1.2) is flagged in the AdaM dataset.

Absolute change from ponesimod baseline is calculated for all post-baseline assessments. All nominal visits are re-windowed based on the visit schedule in Section 5.1.7.

5.4.5.3. Electrocardiogram

It is noted that the criteria to define abnormality in ECG findings has changed during the course of the study, subsequent to the Interim Analysis conducted in 2019, as reflected in the SDTM data.

5.4.5.3.1. 12-Lead ECG

A 12-lead ECG is performed pre-dose at all scheduled visits. In addition, ECGs are pre-dose and hourly post-dose (1h, 2h, 3h, 4h, 5h, 6h) on Day 1, Day 8 and Day 15 of ponesimod intake, at reinitiation visits, and at the visit for the transition from TP2 to TP3. In the event of a clinically relevant change from baseline in HR or other ECG parameters persisting after the 6-hour post-dose monitoring, additional ECGs are performed every 2 hours after 6 hours.

All 12-lead ECG results are stored in SDTM201.EG/SDTM202.EG together with nominal visit and timepoint information. The two EG datasets are concatenated for the purposes of derivations and analysis.

All nominal visits (excluding **post-dose** assessments collected on Day 1, Day 8 and Day 15 of ponesimod administration and at re-initiation visits) are re-windowed based on the visit schedule in Section 5.1.8. All assessments, including post-dose assessments, are used for the derivation of "Last on treatment" and "Last follow-up" values.

For by-visit and by-hour tables presenting summary statistics of quantitative ECG results, the latest (by datetime) transmitted measurement per nominal subject-visit/timepoint is used in case of multiple data available at that visit or visit/timepoint.

ECG parameter measurements

The following parameters are transferred by the central vendor (eRT): heart rate, RR, PR, QRS, QT, and are used as derived by eRT and are not re-calculated.

Corrected QT values QTcF and QTcB are available in SDTM.EG. The derivation based on Fridericia's and Bazett's formulae is as follows:

- $QTcB (ms) = QT (ms)/RR (sec)^{0.5}$
- QTcF (ms) = QT (ms)/RR (sec) $^{1/3}$

These values are then rounded.

The ponesimod baseline values (as described in Section 5.1.2) are flagged in the AdaM dataset.

Absolute and percentage change from ponesimod baseline are derived for all post-baseline assessments.

All nominal visits (excluding post-dose assessments collected on Day 1, Day 8 and Day 15 of ponesimod administration and at re-initiation visits) are re-windowed based on the visit schedule in Section 5.1.8.

All nominal assessments meeting the following conditions are flagged in the AdaM dataset:

- Heart rate ≥ 100 bpm;
- Heart rate ≤ 50 bpm;
- Heart rate \leq 45 bpm;
- Heart rate ≤ 40 bpm;
- PR interval > 200 ms and increase of > 20 ms from to ponesimod baseline assessment;
- QTcF/QTcB prolongation of > 500 ms;
- QTcF/QTcB prolongation of > 480 ms;
- QTcF/QTcB prolongation of > 450 ms;
- QTcF/QTcB increase from ponesimod baseline of > 30 ms;
- QTcF/QTcB increase from ponesimod baseline of > 60 ms;
- QTcF/QTcB prolongation of > 500 ms and increase from ponesimod baseline > 30 ms;
- QTcF/QTcB prolongation of > 500 ms and increase from ponesimod baseline > 60 ms;
- QTcF/QTcB prolongation of > 450 ms and increase from ponesimod baseline > 30 ms;
- QTcF/QTcB prolongation of > 450 ms and increase from ponesimod baseline > 60 ms.

Pre-dose values on Day 1, Day 8 and Day 15 following first ponesimod administration and on Day 1 of a re-initiation are flagged, and absolute and percent change from pre-dose on each day are calculated for the hourly post-dose assessments.

Post-dose assessments on Day 1, Day 8 and Day 15 following first ponesimod administration and on Day 1 of a re-initiation meeting the following conditions are flagged in the AdaM dataset:

- PR interval > 200 ms and increase of > 20 ms compared to pre-dose assessment;
- QTcF/QTcB increase from pre-dose assessment of > 30 ms;
- QTcF/QTcB increase from pre-dose assessment of > 60 ms.

Clinically relevant morphological ECG findings

Morphological ECG findings are reported by the eRT and are mapped to Clinical Data Interchange Standards Consortium (CDISC) standard (code list C71150, with high level categories from code list C71152) in the SDTM.

For analyses in tables the following categories are anticipated:

- Atrioventricular Conduction
- Axis and Voltage
- Chamber Hypertrophy or Enlargement
- Conduction
- Ectopy
- Intraventricular-Intratrial Conduction
- Rhythm Not Otherwise Specified

- ST Segment, T wave, and U wave
- Sinus Node Rhythms and Arrhythmias
- Supraventricular Arrhythmias
- Supraventricular Tachyarrhythmias
- Ventricular Arrhythmias

Findings related to interpretation or technical issues are only included in listings.

Morphological ECG findings are flagged as 'New' if not present at any assessment prior to intake of ponesimod (including assessments taken during the placebo period) or 'Pre-existing' if present at any assessment prior to intake of ponesimod. If a subject has no evaluable ECG assessment prior to first dose of ponesimod, it is conservatively assumed that any treatment-emergent morphological ECG finding is 'New'.

Quantitative ECG parameter measurements

The following summaries are produced for quantitative ECG parameters (heart rate, PR, QRS, QT and QTcF / QTcB) by treatment group:

- Summary of absolute values for ECG parameters: descriptive statistics by analysis visit (AP3 on the PAS);
- Summary of absolute values and absolute change from ponesimod baseline values for ECG parameters: descriptive statistics by analysis visit (AP3 on the PAS);
- Summary of pre- and post-dose absolute values for ECG parameters on nominal Day 1, 8 and 15 relative to first ponesimod administration: descriptive statistics by nominal day and nominal timepoint (PAS)*;
- Summary of absolute values and absolute change from pre-dose values for ECG parameters on nominal Day 1, 8 and 15 relative to first ponesimod administration: descriptive statistics by nominal day and nominal timepoint (PAS)*;
- Incidence of treatment-emergent abnormalities [as defined above]: frequency counts, percentages, where percentages are based on the number of subjects with at least one post-baseline value during the analysis period (i.e., number of subjects at risk) (AP3 on the PAS);
- Incidence of treatment-emergent abnormalities [as defined above] on nominal Day 1 relative to first ponesimod administration: frequency counts, percentages, where percentages are based on the number absolute of subjects with at least one post-dose value on Day 1 (i.e., number of subjects at risk) (PAS)*.
- Incidence of treatment-emergent PR and QTc prolongations (including increase from predose) and HR outliers on Day 1 of treatment re-initiation after treatment interruption

The following plots are produced for ECG parameters (HR, PR, QRS, QT and QTcF / QTcB) by treatment group:

• Plot of pre- and post-dose absolute values for ECG parameters on nominal Day 1, 8 and 15 relative to first ponesimod administration: mean ± SE by nominal day and nominal timepoint (PAS)*;

- Plot of absolute change from pre-dose values for ECG parameters on nominal Day 1, 8 and 15 relative to first ponesimod administration: mean ± SE by nominal day and nominal timepoint (PAS)*.
- Plot of absolute values for heart rate: mean \pm SE by analysis visit (AP3 on the PAS);
- Plot of absolute change from ponesimod baseline values for heart rate: mean ± SE by analysis visit (AP3 on the PAS).

All abnormal ECG parameter results are listed by treatment group and visit based on the PAS.

Summary tables and plots of ECG parameters on nominal Day 1, 8 and 15 relative to first ponesimod administration were presented in the Interim Analysis CSR and are not planned to be presented in the Final CSR.

Incidence of treatment-emergent abnormalities on nominal Day 1 relative to first ponesimod administration were presented in the Interim Analysis CSR and are not planned to be presented in the Final CSR.

Incidence of treatment-emergent PR and QTc prolongations (including increase from pre-dose) and HR outliers on Day 1 of treatment re-initiation after treatment interruption were presented in the Interim Analysis CSR and are not planned to be presented in the Final CSR.

Clinically relevant morphological ECG findings

The following summaries are produced for morphological ECG findings by treatment group:

- Incidence of clinically relevant morphological ECG findings [as defined above], by preferred term: frequency counts and percentages (AP3 on the PAS);
- Incidence of clinically relevant morphological ECG findings on nominal Day 1, Day 8 and Day 15 relative to first ponesimod administration, by nominal day and preferred term: frequency counts and percentages (PAS)*.

*For summaries/plots on nominal Days 1, 8 and 15 following first ponesimod administration, subjects are summarized as follows:

- For nominal Day 1 all subjects are summarized under ponesimod 10 mg;
- For nominal Day 8 subjects randomized to ponesimod 10 mg are summarized under ponesimod 10 mg, whilst subjects randomized to ponesimod 20 mg or ponesimod 40 mg are summarized under ponesimod 20 mg;
- For nominal Day 15 all subjects are summarized under their randomized dose.

This reflects the up-titration scheme and the doses that subjects were receiving at the time.

Post-dose hourly assessments are not included in summaries/plots by visit.

For tables reporting treatment-emergent abnormalities/findings, all assessments are considered, whether scheduled or unscheduled, pre-or post-dose.

All ECG morphological abnormalities are listed by treatment group and visit based on the PAS.

Summary tables and plots of incidence of clinically relevant morphological ECG findings on nominal Day 1, Day 8 and Day 15 relative to first ponesimod administration were presented in the Interim Analysis CSR and are not planned to be presented in the Final CSR.

5.4.5.3.2. 48-hour Holter ECG

Holter ECG is reported in SDTM202.XH. This data is not combined with that of the core, as Holter ECG monitoring is performed only for 4 subjects in Germany during the extension study.

Holter ECG monitoring is performed at Visit E1 (Day 1), Visit E2, Visit E3, Visit E7 (Week 24) and Visit E9 (Week 48) of TP1. For subjects enrolled into TP2, a 48-hour Holter ECG monitoring is performed in case of study drug re-initiation (followed by dose up-titration) on the day of re-initiation and of dose up-titration. Holter ECG monitoring is also performed at the visit for the transition from TP2 to TP3.

The Holter ECG is assessed by eRT as 'Normal' or 'Abnormal'. If 'Abnormal', the specific abnormalities are captured as free-text.

A listing of all Holter ECG data collected during the extension study is provided based on the Holter analysis set.

Holter ECG data was presented in the Interim Analysis CSR and as no new data is expected, is not planned to be presented in the Final CSR.

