1.3.2.4 Safety and tolerability

Clinical studies to date have identified transient changes in heart rate (HR) and atrioventricular (AV) conduction as the most prominent safety-related signal with ponesimod. Oral doses of 5 mg or above resulted in dose-dependent sinus rate reductions in all treated patients; the changes were transient and resolved largely within 6 10 hours after dosing. In some patients, these HR reductions were accompanied by a transient effect on AV conduction with prolongation of the PR interval on the electrocardiogram (ECG) and, occasionally, second degree AV block. The effects on HR and AV conduction diminish with repeated administration of ponesimod, indicating desensitization. To minimize the first-dose effects on HR and AV conduction, a dose uptitration regimen was successfully tested and is implemented in current clinical trials.

Difficulty in inspiration (dyspnea) and related pulmonary function test (PFT) changes have also been detected in humans. Mild transient dyspnea/cough was noted frequently 2 6 h

after an oral dose of 40 mg or higher, and was associated with a clinically relevant forced expiratory volume (FEV_1) decrease from baseline. Symptoms resolved spontaneously upon discontinuation of treatment with ponesimod, and PFTs returned to baseline upon drug discontinuation.

In the long-term clinical studies, an increased incidence of adverse events (AEs) of hypertension was observed in patients with hypertension at baseline, treated with ponesimod.

Elevations of aspartate transaminase (AST) and/or alanine aminotransferase (ALT), without any bilirubin increase have been noted with ponesimod; they were reversible upon discontinuation of dosing. The changes were asymptomatic.

Cases of macular edema associated with changes in visual acuity have been observed in patients treated with ponesimod. These events resolved upon discontinuation of ponesimod.

Safety results from the completed AC-058B301/OPTIMUM study and the interim analysis of the ongoing AC-058B202 study were consistent with previous studies and provide support for the long-term safety of ponesimod. Results of the AC-058B301/OPTIMUM study also support the safety and tolerability of the gradual ponesimod uptitration regimen.

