5.6 Safety and tolerability endpoints

All AEs and SAEs are coded using the MedDRA dictionary.

AEs will be analyzed by treatment groups.

The treatment-emergent AEs will be tabulated by system organ class (SOC) and individual preferred terms within each SOC. AEs will also be tabulated by severity and by relationship to ponesimod. Summary tables will be accompanied by individual patient listings.

Treatment-emergent SAEs will be listed and summarized similarly to AEs.

AEs leading to premature discontinuation of study drug will be listed and summarized by crude incidence rates.

Post-treatment AEs, SAEs, and abnormalities (i.e. occurring from 16 until 30 or 90 days after study drug discontinuation) will be tabulated and/or listed dependent on the observed events.

AEs ongoing at the end of the core study and reported separately on the extension CRF will be listed.

Reasons for premature discontinuation of ponesimod will be listed and summarized by frequency tables.

Reasons for death will be listed and summarized similarly to AEs leading to premature discontinuation.

PFTs and BPs will be summarized by descriptive statistics by timepoint both for the absolute values and for the change from baseline.

The proportion of patients with treatment-emergent ECG abnormalities will be displayed. Absolute values and changes during the course of the study of ECG numeric parameters will be summarized by descriptive statistics.

Treatment-emergent abnormalities as assessed by Standard 2D/Doppler echocardiography will be summarized by treatment group and presented similarly to the AEs. Absolute percentage and change of left ventricular ejection fraction during the course of the study will be summarized by descriptive statistics. Individual patient listings will be provided.

Ponesimod / ACT-128800 / JNJ-67896153 Multiple Sclerosis		EudraCT 2009-011470-15 EDMS-ERI-206617631
Protocol AC-058B202	Confidential	
Version 12		
15 March 2022, page 126/179		

Treatment-emergent laboratory abnormalities will be summarized for each laboratory parameter providing their incidence and frequency. Standard numeric laboratory parameters are transformed to standard units. Absolute values and changes during the course of the study of laboratory parameters values converted to standardized units will be summarized descriptively at the relevant time points.

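### The AP3 tables of ECG and blood-pressure abnormalities pool hourly post-dose monitoring with routine pre-dose readings, so for low heart rate, PR prolongation and possibly low blood pressure a lasting effect cannot be told from the first-dose effect

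*SAP*

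**What the plan says.** **ECG (SAP 5.4.5.3.1).** Monitoring is dense around the first doses: "ECGs are pre-dose and hourly post-dose (1h, 2h, 3h, 4h, 5h, 6h) on Day 1, Day 8 and Day 15 of ponesimod intake", and again at re-initiation and at the change from TP2 to TP3. Protocol 3.11.2.1 adds Visit P1. The incidence tables over AP3 take every reading: "For tables reporting treatment-emergent abnormalities/findings, all assessments are considered, whether scheduled or unscheduled, pre-or post-dose". The table that would isolate the first day is withdrawn: "Incidence of treatment-emergent abnormalities on nominal Day 1 relative to first ponesimod administration were presented in the Interim Analysis CSR and are not planned" for the Final CSR. The Day 1/8/15 summaries, including morphology, and the re-initiation table are withdrawn too.

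**Blood pressure (SAP 5.4.5.2.1).** Assessments meeting a threshold are "flagged in the AdaM dataset for all assessments (whether scheduled or unscheduled, and whether windowed or not". The only summary listed is "Incidence of treatment-emergent blood pressure abnormalities for SBP and DBP: frequency counts and percentages", for AP3 on the PAS.

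**Treatment-emergent period (SAP 5.1.4).** It begins with the first dose, so first-dose monitoring lies inside it.

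**Known first-dose effect (Protocol 1.3.2.4).** "Oral doses of 5 mg or above resulted in dose-dependent sinus rate reductions in all treated patients". The same section says that these changes largely resolve within hours, that some patients also had transient PR prolongation and occasionally second-degree AV block, and that the effects fade with repeated dosing.

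**What the protocol asks for blood pressure (5.6).** "PFTs and BPs will be summarized by descriptive statistics by timepoint both for the absolute values and for the change from baseline".

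**The concern.** One qualifying reading in the hours after a first dose is enough to count a subject in the AP3 row, in the same way as a qualifying reading years later. The study's first objective is long-term safety. For the parameters on which the drug has a known, short-lived initial effect, the Final CSR will hold one number that mixes that effect with whatever persists. No planned table gives the number of subjects with low heart rate or a prolonged PR interval on routine pre-dose ECGs.

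The columns add a second difficulty. AP3 tables group subjects by first randomized dose, while everyone starting ponesimod takes 10 mg on Day 1.

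**Working it through.** The documents state no figure on this point, so there is none to reproduce.

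**1. Which readings enter.** For ECG the SAP says so outright. For blood pressure it follows in two steps: the post-dose readings of Days 1, 8 and 15 and of re-initiation are the ones left out of visit windowing, and flags are set whether or not a reading is windowed. Those readings therefore count.

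**2. Which rows could be affected.**
- ECG, 14 criteria: heart rate at or below 50, 45 and 40 bpm (3) and PR (1) match the described effect. Heart rate of 100 bpm or more (1) and QTc (9) do not.
- Blood pressure, 14 criteria: 6 low, 8 high. The protocol describes no first-dose fall in blood pressure, but SAP Table 13 puts hypotension terms in the adverse-event category for bradyarrhythmia after the first dose. Low blood pressure is therefore only a possible case.

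**3. Share of readings.** The count is for a former placebo subject who starts at E1, using the extension schedule. Initiation post-dose readings: 3 days x 6 = 18. The second figure adds 6 hourly readings each at P1 and at the TP3 transition (12 in all) to the denominator.

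| Follow-up | Pre-dose readings | Initiation share |
|---|---|---|
| ECG, full | 13 (E1-E13) + 37 (P1-P37) + 3 (P41, P45, EOT3) = 53 | 18/71 = 25%; 18/83 = 22% |
| BP, full | 13 + 45 + 1 = 59 | 18/77 = 23%; 18/89 = 20% |
| About 8 years | 13 + 27 = 40 | 18/58 = 31%; 18/70 = 26% |
| Leaves at 48 weeks (E1-E9) | 9 | 18/27 = 67% |
| Leaves at 24 weeks (E1-E7) | 7 | 18/25 = 72% |

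**4. Effect on incidence (assumed inputs).** Let pf be the probability of at least one flag in initiation monitoring and pl the probability of at least one flag at any other time, taken as independent. The table prints 1 - (1 - pf)(1 - pl). The share of flagged subjects flagged only at initiation is pf(1 - pl) divided by that.

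| pf | pl | Printed | Printed / pl | Only at initiation |
|---|---|---|---|---|
| 0.20 | 0.05 | 0.240 | 4.8 | 79% |
| 0.10 | 0.10 | 0.190 | 1.9 | 47% |
| 0.05 | 0.20 | 0.240 | 1.2 | 17% |
| 0.02 | 0.40 | 0.412 | 1.03 | 3% |

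If the same subjects tend to be flagged on both kinds of occasion, the last column falls.

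**5. Dose columns.** SAP 5.1.9 groups all analyses by first randomized dose. The withdrawn tables placed everyone under 10 mg on Day 1, and both the 20 mg and 40 mg groups under 20 mg on Day 8, to follow the up-titration. With those tables gone, a Day 1 event on 10 mg appears under 20 mg or 40 mg.

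**6. Output lists side by side.** SAP 5.4.5.2.1 gives rules for picking readings for by-visit and by-hour blood-pressure tables but lists no such table. The blood-pressure entry in SAP 6.2.3 declares removal only of the Day 1/8/15 and re-initiation outputs. For ECG, the 6.2.3 entry on removed incidence outputs is not confined to Day 1, whereas 5.4.5.3.1 drops only the Day 1 and re-initiation versions.

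**The case against.** A reader might infer that the AP3 incidences are largely first-dose effects, that the rows were settled by 2011 when the last patient entered, or that they overstate the routine figure by some fixed multiple. The documents support none of these.

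- No incidence by time since first dose is given. The protocol reports a fall in heart rate in all patients, not values at or below 50 bpm, and Protocol 1.4.5 describes attenuation from Day 2.
- For the 10 mg group, Days 8 and 15 are mock titrations. Hourly monitoring also recurs at P1, at the TP3 transition and at re-initiation, all after TP2 was introduced in 2012 or later still.
- The protocol's long-term blood-pressure signal is hypertension, which is not a first-dose effect.

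The SAP also has a fair defence. Protocol 5.6 defines treatment-emergent ECG abnormalities with no pre-dose restriction, and the pre-dose/post-dose separation in Protocol 3.10.2 concerns change endpoints. Counting every reading is conservative. By-visit ECG summaries, which show minimum and maximum, and the heart-rate plots leave out hourly readings. Abnormal values are listed by visit, and the Day 1 results are in the interim report. SAP 5.4 also speaks of actual intervention received, though it gives no rule for assigning single readings to the dose taken that day.

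This justifies keeping the any-reading tables. It does not fill the gap: summary statistics and listings give no incidence on routine readings. The missing blood-pressure summary may well be a drafting slip, since 5.4 says safety data over time are shown by analysis visit, but the output list does not include it.

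**Conclusion.** The point holds as a limit on interpretation. For low heart rate, PR prolongation or AV conduction, and possibly low blood pressure, the AP3 incidence cannot be separated from the transient first-dose effect and may be dominated by it. No such claim is made for the QTc, high heart rate or high blood-pressure rows.

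The size is unknown. Under the assumed inputs above, the share of flagged subjects flagged only at initiation runs from 3% to 79%. Initiation readings are a minority for long-treated subjects (20% to 31%) and a majority for those who leave within a year. These counts leave out core-study visits and the mock-titration monitoring of subjects who continued from the core study on ponesimod.

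All objectives are exploratory and no hypothesis test is touched. This is a cheap improvement that would serve the long-term safety objective. The unlisted blood-pressure summary and the mismatch over removed ECG outputs stand independently of it.

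**What to change.** 1. In SAP 5.4.5.3.1 and 5.4.5.2.1, keep the any-reading AP3 incidence tables and add a split: (a) pre-dose readings, scheduled and unscheduled; (b) post-dose monitoring readings (Days 1, 8 and 15, P1, TP3 transition, re-initiation). State in the blood-pressure section which readings count.
2. In block (b), show the dose taken on the day for Days 1 and 8, as the withdrawn tables did, or add a footnote that the columns are first randomized dose.
3. List the by-visit SBP/DBP summary of absolute values and change from baseline as a Final CSR output, or declare its removal in SAP 6.2 with a reason.
4. Reword the ECG entry in SAP 6.2.3 so that it names the Day 1 and re-initiation incidence tables only, or change 5.4.5.3.1 if the AP3 table is also meant to go.

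The cost is SAP wording, one filter on the nominal time point and two extra table blocks. No new data are needed.
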